#### 8.1.3 Treatment with hormones or other chemotherapeutic agents may not be administered except for steroids given for adrenal failure (steroid supplementation should be at physiologic dosing or as described in [section 8.1.10](#)); hormones administered for non-disease-related conditions (e.g., insulin for diabetes); and intermittent use of dexamethasone as an antiemetic in solid tumor protocols.

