- **Neuropathy:** Consider neurology consult for any grade 3 or 4 neuropathy, at the discretion of the treating physician.
- **Pancreatitis:** Patients may develop symptomatic and radiologic evidence of pancreatitis as well as DM and DKA. Lipase elevation may occur with other immune mediated events including colitis, hepatitis, and gall bladder inflammation.
- **Immunosuppressive agents:** Steroids are recommended as first line intervention for the immune related toxicity of these drugs. Steroids should be started prior to obtaining results of any testing, based on clinical indications for steroid initiation. Specifically: Prior to starting corticosteroids or hormone replacement for any reason, appropriate endocrine testing including cortisol, ACTH, TSH and T4 should be obtained to document baseline pituitary function which may be suppressed on treatment. Steroids should be tapered over 1 month if clinically appropriate, while monitoring for any return of toxicity. Potential second line agents are mycophenolate, cyclophosphamide, infliximab, IVIG, etc., at the discretion of the treating physician.
- **Vaccination:** Flu vaccine, pneumococcal vaccine, and any other relevant vaccines are recommended PRIOR to initiation of protocol therapy, at the discretion of the treating physician.

**8.1.11 Fatigue:** Fatigue is the most common adverse event associated with immune checkpoint therapy. Consider evaluation for associated or underlying organ involvement including pituitary disease, thyroid disease, and liver disease, or muscle inflammation

**8.1.12 Fever:** Patients may experience isolated fever during infusion reactions or up to several days after infusion. Continued fever over the course of 1-2 weeks may represent autoimmune events, or infection. Appropriate workup should be initiated, at the discretion of the treating physician.

**8.1.13 Supplementation:** Electrolyte abnormalities should be adequately corrected with appropriate supplementation upon discovery.

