## 8.2 Dose Modifications

- If study drug/s is(are) held for >6 weeks, study drug/s will be discontinued.
- Any patients with autoimmune toxicity who require additional immune suppressive treatment beyond steroids should go off study drug/s.
- Patients may be dose-delayed for toxicity evaluation and restarted depending on results.
- Any patient started on corticosteroids initially for a presumed autoimmune adverse event, and subsequently found to not have an autoimmune etiology of their adverse event, may resume therapy after a 2 week observation period without recurrence of symptoms.
- Study drug/s should not be restarted until steroids have been tapered down to 5mg of prednisone equivalent.
- Patients requiring > two dose delays for the same event should go off study drug.
- Descriptors below utilize CTCAE version 4.03. AERs reporting may be required for some adverse events (See [Section 9.0](#))

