### 8.2.2 Dose Modification

Skin Rash and Oral Lesions	Management/Next Dose for Nivolumab and Ipilimumab
Grade 1	Continue on protocol therapy*
Grade 2	Continue on protocol therapy.*
Grade 3	Hold** until ≤ Grade 1. Resume nivolumab/ipilimumab at same level*
Grade 4	Off protocol therapy
*Steroid use does not require discontinuation of protocol therapy.	
**Any grade Steven Johnson syndrome requires discontinuation of protocol therapy.	
Recommended management: See Skin AE management algorithm	

Liver Function ALT AST Bilirubin	Management/Next Dose for Nivolumab and Ipilimumab
Grade 1	Continue protocol therapy*
Grade 2	Hold therapy until ≤ grade 1 then restart nivolumab/ipilimumab at same dose.*
Grade 3	Off protocol therapy
Grade 4	Off protocol therapy
*Steroid use does require discontinuation of protocol therapy.	
Recommended management: see Hepatitis AE management algorithm	

Colitis**	Management/Next Dose for Nivolumab and Ipilimumab
Grade 1	Continue protocol therapy*
Grade 2	Hold therapy until $\leq$ Grade 1*, then restart nivolumab at same dose. Discontinue ipilimumab.
Grade 3	Off protocol therapy.
Grade 4	Off protocol therapy.
See GI AE Algorithm for management of symptomatic colitis. *Steroid use does not require discontinuation of protocol therapy. **Follow this table for diarrhea when the workup shows objective evidence of autoimmune colitis.	
Recommended management: see GI AE management Algorithm	

Diarrhea**	Management/Next Dose for Nivolumab and Ipilimumab
Grade 1	Continue protocol therapy
Grade 2	Hold until $\leq$ Grade 1*, then restart nivolumab/ipilimumab at same dose.
Grade 3	Hold until $\leq$ Grade 1*, then restart nivolumab/ipilimumab at same dose.
Grade 4	Hold until $\leq$ Grade 1*, then restart nivolumab/ipilimumab at same dose.
*Steroid use does not require discontinuation of protocol therapy. **Follow this table for diarrhea when the workup shows no objective evidence of autoimmune colitis	

Pancreatitis**	Management/Next Dose for Nivolumab and Ipilimumab
Grade 2	Continue on protocol therapy*
Grade 3	Hold therapy until $\leq$ grade 2 then restart nivolumab/ipilimumab at same dose.*
Grade 4	Off protocol therapy
*Steroid use does require discontinuation of protocol therapy. **Patients who have asymptomatic amylase or lipase elevation may have a self-limited course and may continue therapy.	

Pneumonitis	Management/Next Dose for Nivolumab and Ipilimumab

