Grade 1	Hold dose pending evaluation. Resume nivolumab/ipilimumab if lymphocytic pneumonitis is excluded.*
Grade 2	Hold until $\leq$ Grade 1*, then restart nivolumab/ipilimumab at same dose.
Grade 3	Off protocol therapy.
Grade 4	Off protocol therapy
*Steroid use does require discontinuation of protocol therapy.	
Recommended management: See Pulmonary Adverse Event Management Algorithm	

Gastritis, nausea, vomiting	Management/Next Dose for Nivolumab and Ipilimumab
Grade 1	Continue protocol therapy*
Grade 2	Hold pending evaluation for gastritis duodenitis and other immune adverse events or other causes. Resume nivolumab/ipilimumab at same dose level after resolution to Grade $\leq$ 1.*
Grade 3	Hold pending evaluation until $\leq$ Grade 1. Resume nivolumab at same dose level.* If symptoms do not resolve within 7 days with symptomatic treatment, patients should go off nivolumab. Discontinue ipilimumab.
Grade 4	Off protocol therapy
*Steroid use does not require discontinuation of protocol therapy.	

Fatigue	Management/Next Dose for Nivolumab and Ipilimumab
Grade 1	Continue protocol therapy.
Grade 2	Continue protocol therapy.
Grade 3	Hold until $\leq$ Grade 2. Resume nivolumab/ipilimumab at same dose level.*
*Steroid use does not require discontinuation of protocol therapy.	

Neurologic events **	Management/Next Dose for Nivolumab and Ipilimumab
Grade 1	Hold dose pending evaluation. Once evaluation is complete, resume nivolumab/ipilimumab at same dose level.*
Grade 2	Hold dose pending evaluation and observation. Hold until $\leq$ Grade 1 and then resume nivolumab/ipilimumab at same dose level.*
Grade 3	Off protocol therapy
Grade 4	Off protocol therapy
*Steroid use does require discontinuation of protocol therapy. **Patients with any grade CNS events of aseptic meningitis, encephalitis, symptomatic hypophysitis, or myopathy, polymyositis, rhabdomyolysis, peripheral demyelinating neuropathy, cranial neuropathy (other than peripheral n. VII), GB syndrome, myasthenia gravis should be off study once diagnosed.	
Recommended management: See Neurologic Adverse Event Management Algorithm	

Endocrine Toxicity**	Management/Next Dose for Nivolumab and Ipilimumab
Grade 1	Continue protocol therapy.*
Grade 2	Hold until $\leq$ Grade 1 and patients are on a stable replacement hormone regimen, then resume nivolumab/ipilimumab at same dose level.*
Grade 3	Off protocol therapy.***

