Grade 4	Off protocol therapy
*Steroid use for isolated thyroid disease or testosterone deficiency does not require discontinuation of protocol therapy. Steroid use for any other form of endocrine toxicity does require discontinuation of therapy. **Note all patients with symptomatic pituitary enlargement, exclusive of hormone deficiency, but including severe headache or enlarged pituitary on MRI should be considered grade 3 events and removed from protocol therapy. Also, note patients with thyroiditis may be retreated with immunotherapy while on replacement therapy. ***Isolated thyroid or testosterone deficiency may be treated as grade 2 if there are no other associated deficiencies and adrenal function is monitored.	
Recommended management: See Endocrine Management Algorithm	

Fever	Management/Next Dose for Nivolumab
Grade 1	Continue protocol therapy. May hold if needed for evaluation, then resume nivolumab/ipilimumab at same dose level.*
Grade 2	Hold until $\leq$ Grade 1. Resume nivolumab/ipilimumab at same dose level.*
Grade 3	Hold until $\leq$ Grade 1. Resume nivolumab/ipilimumab at same dose level.*
Grade 4	Off treatment
*Steroid use does not require discontinuation of protocol therapy.	
See Appendix V regarding infusion reactions.	

Renal toxicity: Creatinine increased, hematuria	Management/Next Dose for Nivolumab and Ipilimumab
Grade 1	Continue protocol therapy.*
Grade 2	Hold until $\leq$ Grade 1. Resume nivolumab/ipilimumab at same dose level.*
Grade 3	Off protocol therapy.
Grade 4	Off protocol therapy
*Steroid use does require discontinuation of protocol therapy.	
Recommended management: AE management guidelines	

Infusion Reaction	Management/Next Dose for Nivolumab and Ipilimumab
Grade 1	Continue protocol therapy.*
Grade 2	Hold until $\leq$ Grade 1. Resume nivolumab/ipilimumab at same dose level.*
Grade 3	Off protocol therapy.
Grade 4	Off protocol therapy
*Steroid use does not require discontinuation of protocol therapy.	
Recommended management: see Section 8.1.9 and Appendix V management guidelines	

Cardiac *	Management/Next Dose for BMS-936558 (Nivolumab) + Ipilimumab Cardiac Toxicities

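### Section 8 does not say whether therapy stops or resumes when steroids were given for an event that proves non-autoimmune, or as physiologic endocrine replacement

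*Combined protocol and SAP*

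**What the plan says.** **Non-autoimmune events.** The liver, pancreatitis, pneumonitis, neurologic and renal tables in Section 8.2.2 each carry the footnote "Steroid use does require discontinuation of protocol therapy". It has no exception. Section 8.2, in the general bullets ahead of the tables, covers any patient started on corticosteroids for a presumed autoimmune event later found to have another cause. That patient "may resume therapy after a 2 week observation period without recurrence of symptoms". The bullet names no event type and excludes none.

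**Endocrine events.** The Grade 2 row holds treatment until the event improves to Grade 1 or less and "patients are on a stable replacement hormone regimen, then resume nivolumab/ipilimumab at same dose level". The asterisk on that row leads to a footnote. It exempts steroids for isolated thyroid disease or testosterone deficiency and then adds: "Steroid use for any other form of endocrine toxicity does require discontinuation of therapy".

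**Related text.** Section 8.1.10 says of immune toxicity: "Steroids should be started prior to obtaining results of any testing, based on clinical indications for steroid initiation". Appendix III advises continuing immunotherapy when the cause is non-inflammatory. Section 8.1 describes those algorithms as recommended guidelines.

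**The concern.** A site could face either situation and find two instructions with opposite outcomes. The first is foreseeable. Section 8.1.10 lets steroids start before test results are back where clinically indicated, allows them for pneumonitis of any grade, and calls inflammatory pneumonitis often a diagnosis of exclusion. Some patients may therefore receive steroids for an event that the work-up attributes to something else.

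The stake is how long patients are treated and how safety events are handled. One reading ends therapy for an event that was not immune-mediated. The other re-exposes a patient whom the table's footnote removes. Removal is also hard to undo for Arm 1. Section 3.4.2 bars re-registration for patients removed for any reason other than progression, and Section 12.2 limits crossover in the same way, so an Arm 1 patient taken off under a footnote also loses access to the combination.

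**Working it through.** No arithmetic is involved beyond a count, so the check sets the texts side by side.

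**1. Count of Section 8.2.2 tables by steroid footnote**

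| Footnote | Tables | Number |
|---|---|---|
| Steroid use ends therapy | liver, pancreatitis, pneumonitis, neurologic, renal | 5 |
| Steroid use does not end therapy | skin, colitis, diarrhea, gastritis/nausea/vomiting, fatigue, fever, infusion reaction | 7 |
| Mixed | endocrine | 1 |
| No steroid footnote | cardiac, all other events | 2 |

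Total: 5 + 7 + 1 + 2 = 15. Tables concerned: 5 + 1 = 6. The seven tables in the second line say the reverse: "Steroid use does not require discontinuation of protocol therapy".

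**2. The patient who falls under both rules.** Suppose suspected Grade 1 pneumonitis, steroids started, and lymphocytic pneumonitis then excluded.
- The Section 8.2 bullet allows resumption after two weeks.
- The Grade 1 row allows resumption once lymphocytic pneumonitis is excluded.
- The asterisk on that same row leads to the footnote that ends therapy for steroid use.

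The same pair of rules applies in the other four tables whenever the presumed immune event proves to be something else.

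**3. Is precedence stated?** No. The tables are introduced as the protocol-specific instructions for continuing the agents, which favours the footnotes. The bullet is the more specific text for this patient, which favours resumption. Appendix III supports resumption in its hepatic, neurologic, pulmonary and renal algorithms, which match four of the five tables (none for pancreatitis). As recommended guidance that does not mention the footnote, it does not settle the order.

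**4. Endocrine Grade 2.** A patient with adrenal insufficiency may have a steroid as the replacement hormone. The row makes stable replacement the condition for resuming. The footnote ends therapy for steroid use in endocrine toxicity other than the two exempt conditions. Whether replacement at physiologic dose is steroid use in that sense is not stated.

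**5. Which grades are affected.** In the liver, pneumonitis, neurologic and renal tables, Grades 3-4 go off therapy whatever the steroid use, so the footnote decides only Grades 1-2. In pancreatitis, Grade 2 continues, Grade 3 is held and restarted, and Grade 4 goes off, so Grade 3 is affected as well. Endocrine Grades 3-4 go off, apart from the exception for isolated thyroid or testosterone deficiency.

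**6. Effect on the primary analysis.** Section 13.3 counts every eligible, consented patient who began treatment as evaluable and analyses by randomized arm. Stopping or resuming does not change the denominator.

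**The case against.** The strongest reply is that the text already reads coherently. The steroid rule is set event by event, and within a table the asterisk qualifies the row: resume, unless steroids were needed. The Section 8.2 bullet is then an exception for events that prove non-autoimmune, and Appendix III agrees with it. For endocrine events, row and footnote fit together if the Grade 2 row is taken to mean thyroid or testosterone replacement only. Early steroids depend on clinical indication, and for pneumonitis they are discretionary.

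Much of this stands. Most steroid-treated patients have a workable reading, and the example is possible rather than instructed. But the coherent reading is not the only one. A site that treats the tables as the controlling instructions reaches the opposite result for the same patient, and no sentence rules that out. The endocrine reading likewise needs a limit that the row does not state.

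Two further passages might seem to sharpen the contradiction, but they do not:
- Section 8.2 says "Study drug/s should not be restarted until steroids have been tapered down to 5mg of prednisone equivalent". This is a condition for restarting, not a permission, and it fits the seven tables in which steroids do not end therapy.
- Section 8.1.3 bars hormones "except for steroids given for adrenal failure (steroid supplementation should be at physiologic dosing" or as Section 8.1.10 describes, with further exceptions. This is a concomitant-medication rule and does not address resuming after toxicity. It also has a separate use, because Appendix IV admits patients whose endocrine deficiencies are managed with physiologic corticosteroids.

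**Conclusion.** The point holds for two situations: steroids given for a presumed immune event in one of the five tables that proves non-autoimmune, and physiologic steroid replacement in Grade 2 endocrine toxicity. In the first, two stated rules give opposite outcomes and their order is missing. In the second, a term is undefined. That discontinuation is lasting is an inference, since the footnote does not say so; the contrast with holding a dose and the re-registration bar in Section 3.4.2 support it.

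The number of affected patients cannot be estimated, because the documents give no steroid-use rate and no rate of work-ups that end in a non-autoimmune diagnosis. A reader might infer more than the documents support:
- **That steroid use in general is both a reason to stop and a state from which to resume.** The event-by-event footnotes do not say that.
- **That the cited Grade 3-4 related rates of 43% (renal cell carcinoma, Section 1.6) and 53% (concurrent combination regimen, Section 1.5) measure the problem.** They are not steroid-use rates, and the affected patients are mainly Grade 1-2. Section 1.5 attributes most of the 53% to skin rash, where steroids do not end therapy.
- **That one patient could reverse the verdict in a 12-patient arm judged on two responses.** That is true of any deviation in so small an arm and shows nothing particular to this one.
- **That the primary endpoint is compromised.** Evaluability is unchanged. Uneven exposure could affect response and adverse event rates, but the documents give nothing with which to size this.

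The consequence is therefore inconsistent exposure and safety handling, plus loss of crossover for Arm 1 patients taken off.

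**What to change.** Reconcile the passages in Section 8 on two points:
1. For the liver, pancreatitis, pneumonitis, neurologic and renal tables, state whether the Section 8.2 bullet or the table footnote prevails when steroids were started for a presumed autoimmune event that proves not to be one. Make the asterisk on the Grade 1 pneumonitis row, and the wording in Appendix III, agree with the answer.
2. In the endocrine footnote, state whether physiologic steroid replacement counts as steroid use, so that the Grade 2 row and its footnote give one answer.

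The sponsor decides which rule stands in each case; this review takes no position on that. The cost is a wording change in the next protocol update, with no new data, procedures or change to the design.

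### Section 8.2.2 gives conflicting stop and retreat instructions for symptomatic hypophysitis that presents as hormone deficiency, and its off-study wording does not match the required follow-up

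*Combined protocol and SAP*

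**What the plan says.** Section 8.2.2 sets out dosing instructions in one table per toxicity. Two of these tables bear on hypophysitis.

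- **Neurologic events, double-asterisk footnote.** It lists diagnoses that override the graded rows. The list opens "Patients with any grade CNS events of aseptic meningitis, encephalitis, symptomatic hypophysitis" and closes "GB syndrome, myasthenia gravis should be off study once diagnosed". The graded rows above it use different words for stopping: Grades 3 and 4 go off protocol therapy.
- **Endocrine toxicity, graded rows.** Grade 1 reads "Continue protocol therapy". Grade 2 is held until it improves to Grade 1 or less and "patients are on a stable replacement hormone regimen, then resume nivolumab/ipilimumab at same dose level". Grades 3 and 4 go off protocol therapy.
- **Endocrine toxicity, double-asterisk footnote.** It covers "all patients with symptomatic pituitary enlargement, exclusive of hormone deficiency", "including severe headache or enlarged pituitary on MRI should be considered grade 3 events and removed from protocol therapy".
- **Endocrine toxicity, single-asterisk footnote.** Steroids for isolated thyroid disease or testosterone deficiency do not force a stop, but "Steroid use for any other form of endocrine toxicity does require discontinuation of therapy".
- **Endocrine toxicity, triple-asterisk footnote, on the Grade 3 row.** "Isolated thyroid or testosterone deficiency may be treated as grade 2", provided no other deficiency is present and adrenal function is monitored.

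On follow-up, the triple-asterisk footnote to the Section 5.0 calendar keeps patients removed for toxicity under six-monthly follow-up for survival and disease status. Section 12.1.3 requires survival follow-up for anyone who stops study agent other than by withdrawing consent. Section 12.4 requires endpoint follow-up when therapy stops because the protocol's constraints harm the patient's health.

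**The concern.** The neurologic footnote stops symptomatic hypophysitis at every grade. The endocrine table's removal footnote is worded around pituitary enlargement and sets hormone deficiency aside, so a deficiency presentation falls to the graded rows, where Grades 1 and 2 stay on or return to treatment. No cross-reference or order of precedence connects the two tables.

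A site has good reason to open the endocrine table first. Both risk lists in Section 9.4 place hypophysitis under endocrine disorders. The nursing guidelines in Sections 10.2 and 10.3 group it with the endocrinopathies and describe patients whose only complaint may be vague fatigue. The instruction to stop sits in a footnote to a different table.

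At stake is whether a patient with an immune toxicity listed for both agents is stopped or retreated. Two sites, each following the protocol, could manage the same patient differently. That would change exposure and time on treatment in either arm and after crossover. A second, smaller issue is that the neurologic footnote speaks of leaving the study, while elsewhere the protocol distinguishes leaving treatment from leaving follow-up.

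**Working it through.** No figure in the plan is involved. The check is a comparison of the two tables, case by case, for a patient diagnosed with symptomatic hypophysitis.

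| Presentation | Neurologic footnote | Endocrine table | Result |
|---|---|---|---|
| Pituitary enlarged on MRI, or severe headache | Stop | Counted as Grade 3, removed | Agree |
| Steroid-treated endocrine toxicity other than isolated thyroid disease or testosterone deficiency | Stop | Discontinue (single-asterisk footnote) | Agree |
| Grade 3 or 4, outside the triple-asterisk exception | Stop | Off protocol therapy | Agree |
| Grade 1 hormone deficiency, no enlargement, severe headache or steroid use | Stop | Continue | Conflict |
| Grade 2 hormone deficiency, same conditions | Stop | Hold, then resume on stable replacement | Conflict |
| Grade 3 isolated thyroid or testosterone deficiency meeting the triple-asterisk conditions | Stop | May be handled as Grade 2 | Can conflict |
| Grade 1 or 2 deficiency needing physiologic corticosteroid replacement | Stop | Depends on whether replacement is steroid use | Unclear |

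Two rows need comment.

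1. The Grade 3 row assumes that a pituitary cause with only thyroid or testosterone deficiency may be called isolated. The table does not say so. On that same reading, the single-asterisk exemption also means that steroid use would not remove the conflict in the Grade 1 and 2 rows.
2. For the last row, the Grade 2 instruction relies on replacement hormones, while the single-asterisk footnote makes steroid use a reason to stop for most endocrine toxicity. It does not say whether physiologic replacement counts. If it does, the area of conflict shrinks. If it does not, the conflict extends to these patients.

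For the second issue, the wording compares as follows. The neurologic footnote says off study. The graded neurologic and endocrine rows say off protocol therapy. The endocrine footnote says removed from protocol therapy. The general rules in Section 8.2 speak of going off study drug. Sections 5.0, 12.1.3 and 12.4 all continue follow-up after treatment stops. The neurologic footnote therefore differs both from the neighbouring wording and from the follow-up rules.

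**The case against.** The strongest case on the other side is that the tables can be read together. The neurologic footnote speaks of CNS events, and the endocrine footnote separates enlargement from hormone deficiency. On that reading, mass-effect presentations stop and hormone deficiency follows the endocrine grades. Alternatively, the neurologic list is a named-diagnosis override, like the any-grade Stevens-Johnson rule under the skin table, and prevails over any graded row. Both readings are reasonable, but they give opposite answers for the deficiency presentation and the text states neither. The endocrine algorithm in Appendix III is a figure absent from the text available for this review, so what it adds could not be checked. Section 8.1 describes the algorithms as recommended guidelines.

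Three stronger conclusions that a reader might draw are not supported.

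- **That the tables are opposed for symptomatic hypophysitis in general.** They agree in the first three rows of the comparison above.
- **That about 3 to 19 dual-arm patients are affected.** This comes from 195/2 = 97.5 patients, taken as 97, with 0.03 × 97 = 2.9 and 0.20 × 97 = 19.4. The risk lists put hypophysitis in a column headed at most 20% and state no lower limit for it. The 3% belongs to a separate column for rare but serious events. The range would also count all hypophysitis, whereas only the deficiency presentation is in conflict.
- **That follow-up data will be lost.** Sections 5.0, 12.1.3 and 12.4 already require follow-up, so a loss would need a site to take two words literally against three other provisions.

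**Conclusion.** The contradiction is real but confined to symptomatic hypophysitis presenting as hormone deficiency, without pituitary enlargement or severe headache and without steroid use that itself requires stopping. For that presentation, one table stops treatment at any grade and the other continues or resumes it at Grades 1 and 2, with a possible extension to Grade 3 isolated deficiency. Whether physiologic corticosteroid replacement counts as steroid use is left open and moves the boundary.

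The number of patients concerned cannot be derived from the documents. They give no frequency by grade, symptoms, form of presentation or steroid use. No effect on the primary test, the decision thresholds or the sample size is shown. The point still warrants correction because it concerns when treatment must stop for an immune toxicity and the correction is nearly free.

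The off-study phrase is inconsistent wording, not a demonstrated loss of response, progression or survival data.

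This conclusion rests on the tables as printed, and on no precedence rule being given in the endocrine algorithm figure.

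**What to change.** Reconcile the neurologic footnote and the endocrine table so that one stated rule governs hypophysitis and the other table refers to it. The rule should say how it applies by grade, to hormone-deficiency presentations and to isolated thyroid or testosterone deficiency, and whether physiologic corticosteroid replacement is steroid use for the single-asterisk footnote. Which clinical rule to adopt is for the study team.

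In the neurologic footnote, replace the off-study wording with the off-protocol-therapy wording of the graded rows, so that it matches the follow-up in Sections 5.0, 12.1.3 and 12.4.

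The cost is a few lines of text in an amendment. No new data, analysis or sample-size change is needed.

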<math>\leq</math> Grade 1	Hold dose pending evaluation and observation.** Evaluate for signs and symptoms of CHF, ischemia, arrhythmia or myositis. Obtain history EKG, CK (for concomitant myositis), CK-MB. Repeat troponin, CK and EKG 2-3 days. If troponin and labs normalize may resume therapy. If labs worsen or symptoms develop then treat as below. Hold pending evaluation.
Grade >2 with suspected myocarditis	Hold dose.** Admit to hospital. Cardiology consult. Rule out MI and other causes of cardiac disease. Cardiac Monitoring. Cardiac Echo. Consider cardiac MRI and cardiac biopsy. Initiate high dose methylprednisolone. If no improvement within 24 hours, add either infliximab, ATG or tacrolimus. Consult algorithm for more details. Resume therapy if there is a return to baseline and myocarditis is excluded or considered unlikely.
Grade >2 with confirmed myocarditis	Off protocol therapy. Admit to CCU (consider transfer to nearest Cardiac Transplant Unit). Treat as above. Consider high dose methylprednisolone. Add ATG or tacrolimus if no improvement. Off treatment.
*Including CHF, LV systolic dysfunction, Myocarditis, CPK, and troponin	
**Patients with evidence of myositis without myocarditis may be treated according as “other event”	
Note: The optimal treatment regimen for immune mediated myocarditis has not been established. Since this toxicity has caused patient deaths, an aggressive approach is recommended.	

ALL OTHER EVENTS (Note 1)	Management/Next Dose for Nivolumab and Ipilimumab
≤ Grade 1	No change in dose
Grade 2	Hold until ≤ Grade 1, then resume nivolumab/ipilimumab at same dose level.
Grade 3	Off protocol therapy (exceptions noted below in note 2)
Grade 4	Off protocol therapy

Note: 1. Modifications are applicable to toxicity that is deemed related to study drug (attribution of possible, probable, or definite).
 
Note 2. For any grade 2 drug-related uveitis or eye pain or blurred vision that does not respond to topical therapy and does not improve to Grade 1 severity within the re-treatment period OR requires systemic treatment, nivolumab and ipilimumab should be discontinued.
	
Recommended management: As clinically indicated	

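### The cardiac dose table appears to skip Grade 2 myocarditis (probably a lost ≥ sign) and has no any-grade stop for confirmed myocarditis

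*Combined protocol and SAP*

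**What the plan says.** Section 8.2.2 gives one table per toxicity. The cardiac table names myocarditis in its scope footnote and has three rows:

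- **≤ Grade 1.** Hold, evaluate, and repeat troponin, CK and EKG after 2-3 days. Then: "If troponin and labs normalize may resume therapy". Also: "If labs worsen or symptoms develop then treat as below".
- **Grade >2, myocarditis suspected.** Hold, admit, start high-dose methylprednisolone, and add a second agent if there is no improvement within 24 hours. Then: "Resume therapy if there is a return to baseline and myocarditis is excluded or considered unlikely".
- **Grade >2, myocarditis confirmed.** The heading as extracted is the word Grade, a greater-than sign, and "2 with confirmed myocarditis". The action is "Off protocol therapy. Admit to CCU (consider transfer to nearest Cardiac Transplant Unit" and further inpatient treatment.

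A note to the table adds: "Since this toxicity has caused patient deaths, an aggressive approach is recommended". A footnote sends only one related group to another table: "Patients with evidence of myositis without myocarditis may be treated according as" an other event.

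The general rules at the start of Section 8.2 apply to all toxicities. The most relevant is: "Any patients with autoimmune toxicity who require additional immune suppressive treatment beyond steroids should go off study drug/s". Drug also stops after a hold of more than 6 weeks or more than two delays for the same event. It may not restart until steroids are down to 5 mg prednisone equivalent. Section 8.2.1 allows no dose reductions.

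**The concern.** The row that takes a patient off treatment for confirmed myocarditis starts above Grade 2, and the row before it ends at Grade 1. Read literally, a patient who first presents with Grade 2 myocarditis, suspected or confirmed, has no instruction in the table written for that event. If the site then falls back on the general table for all other events, the Grade 2 rule there is to hold and then resume at the same dose, which means full-dose rechallenge after an event the protocol itself describes as having been fatal.

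A second, separate point concerns the ≤ Grade 1 row. It releases the patient on laboratory normalization alone, whereas the suspected row also asks that myocarditis be excluded or judged unlikely. The protocol writes explicit any-grade stops for some other serious immune events: Stevens-Johnson syndrome in the skin table, and a list including encephalitis, polymyositis and myasthenia gravis in the neurologic table. Myocarditis has none.

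**Working it through.** No power or sample-size figure is involved. The check is whether every grade has a rule, and whether any other rule closes the gap.

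**1. Grade coverage as extracted.** The bands are {≤1} and {>2}, that is, 3 and above. The grade left out is exactly 2. Headings that include Grade 2: 0 of 3.

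**2. Comparison with the other tables.** Section 8.2.2 has 15 tables: skin, liver, colitis, diarrhea, pancreatitis, pneumonitis, gastritis/nausea/vomiting, fatigue, neurologic, endocrine, fever, renal, infusion reaction, cardiac, and all other events. A Grade 2 rule is printed in 14 of 15, the cardiac table being the exception.

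**3. Other stop rules.** The test case is Grade 2 at first presentation, confirmed, and settling on steroids alone.

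| Rule | Effect in the test case |
|---|---|
| 8.2: immune suppression beyond steroids | Not triggered |
| 8.2: hold of more than 6 weeks | Triggered only if the hold runs that long |
| 8.2: no restart above 5 mg prednisone equivalent | Delays restart; ends therapy only through the 6-week rule |
| 8.2: more than two delays for the same event | Not triggered by one episode |
| 8.2.2 neurologic any-grade list | Myocarditis is not named |
| 8.2.2 footnote that steroid use requires discontinuation | In 5 tables (liver, pancreatitis, pneumonitis, neurologic, renal), and in qualified form in the endocrine table; absent from the cardiac table |
| 8.2.2 all other events, Grade 2 | If used as a fallback, permits resumption at the same dose |
| 7.0 unacceptable toxicity; 12.4 | Permit stopping on judgement; do not require it for this event |
| Appendix III | Seven algorithms by heading, none cardiac |

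**4. The 6-week rule.** Section 8.1.10 suggests tapering steroids over 1 month, about 4.3 weeks. If the hold is counted from the start of steroids (an assumption, since the protocol does not define the start), 6 − 4.3 = about 1.7 weeks remain for work-up and the high-dose phase. Restart within 6 weeks is therefore possible but not assured. A slower course ends therapy.

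**5. Corrected sign.** With Grade ≥2 in both lower rows the bands are {≤1} and {≥2}, and every grade is covered. Confirmed Grade 2 myocarditis is then off therapy, and suspected Grade 2 is held, admitted and worked up. Tables with a Grade 2 rule: 15 of 15.

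**6. What the sign does not change.** The condition for resuming in the ≤ Grade 1 row is normal troponin and laboratory values. In the suspected row it is a return to baseline and myocarditis excluded or thought unlikely. No line ends therapy for confirmed myocarditis irrespective of grade.

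**The case against.** The strongest reply is that the gap rests on one character. The row labels are underlined, and an underlined > looks like ≥ on the page, so the bar may have been lost in reading the PDF. The table itself favours ≥2. The ≤ Grade 1 row sends a worsening patient to the rows below, and the next step up from Grade 1 is Grade 2; under a strict >2, that patient would be sent to rows that exclude them. The protocol is also loose with comparators elsewhere. Creatinine is <1.5 × ULN in the front summary and ≤1.5 × ULN in Section 3.3.9; clearance is ≥45 and >45 mL/min in the same two places; the crossover baseline scan is <28 days in Section 5.0, footnote E, and within 28 days in Section 11.1. This all stands, and it is why the first step is to check the source. It does not prove that the bar was lost in reading, since ≤ survives in the first cardiac row.

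It can also be said that an any-grade stop is a preference, since nothing requires uniform rules across organ tables, and that the ≤ Grade 1 row already demands a hold, evaluation and repeat tests. That is fair. The case for the extra line is consistency with the two other tables and the protocol's own note on deaths.

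Last, the cardiac table refers to an algorithm, and Section 8.1 points to the Investigator Brochure, which is not available here. Sites may have had clearer instructions there.

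A reader might infer that nothing stops therapy in steroid-responsive Grade 2 myocarditis. The documents do not support that: the 6-week rule ends therapy whenever recovery and taper run long, and Sections 7.0 and 12.4 leave the investigator free to stop.

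**Conclusion.** The point holds in a limited form, as a minor safety-text correction.

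- **Grade 2 gap.** It exists in the extracted text and probably reflects a missing bar. If the source does print >, what is left uncovered is confirmed myocarditis that is Grade 2 at first presentation, settles on steroids alone, and reaches 5 mg prednisone equivalent within 6 weeks. No event-specific rule then requires stopping.
- **≤ Grade 1 row.** The absence of a requirement to exclude myocarditis, and of an any-grade stop, remains whichever sign is correct.

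It would go too far to conclude that the plan intends rechallenge after Grade 2 myocarditis. Nothing states such an intention, and the escalation sentence and the note on an aggressive approach point the other way.

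The number of patients affected cannot be given. Section 9.4 lists myocarditis as rare but serious for each agent, but the documents give no Grade 2 rate and no rate for the combination. The conclusion assumes that the Investigator Brochure does not supply the missing rule. Endpoint, sample size and analysis are untouched.

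**What to change.** 1. Check the sign in both lower cardiac headings against the source document.
2. Make them read Grade ≥2 with suspected myocarditis and Grade ≥2 with confirmed myocarditis.
3. Add one line to the cardiac table: confirmed myocarditis of any grade, off protocol therapy. This matches the any-grade stops in the skin and neurologic tables and settles the ≤ Grade 1 case whatever the source sign proves to be.

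The cost is two headings and one line in the next protocol update. The clinical price is that a rare patient with mild confirmed myocarditis loses the option of rechallenge.
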